1. INTRODUCTION

The purpose of this study is to evaluate the use of Raplixa in the pediatric surgical population. This study will be conducted in compliance with Good Clinical Practices (GCP) including the Declaration of Helsinki and all applicable regulatory requirements.

1.1. BACKGROUND

The use of topical hemostats, such as fibrin sealants comprising plasma-derived fibrinogen mixed with biologically active thrombin, has been reported since the mid-1940s (1). Commercially-available fibrin sealants have been licensed in the United States and provide an alternative approach to achieve hemostasis during surgical procedures when bleeding cannot be controlled by standard surgical or mechanical techniques (2-6). Fibrin sealants mimic the last stage of the human coagulation system to support local hemostasis as they generate semi-rigid, cross-linked fibrin clots that bind the surface of injured tissues to seal surfaces, support sutures, and/or improve repair or healing of the tissues. The mechanism of action of Raplixa, like that of other fibrin sealants, is based on thrombin's enzymatic activity that catalyzes the conversion of fibrinogen into fibrin monomers that polymerize spontaneously to form a fibrin clot. The thrombin in Raplixa also activates endogenous factor XIII which crosslinks fibrin to create a firm and dissolution-resistant clot that promotes local and rapid hemostasis at the site of application. Because Raplixa dissolves in blood at the bleeding site, blood cells, platelets, and circulating plasma proteins are incorporated into the clot that resembles the natural fibrin clot that is formed during endogenous blood coagulation. As with other fibrin sealants, Raplixa is degraded and metabolized similar to the process by which intrinsic degradation of natural clots of fibrinogen and thrombin occurs.

Raplixa and the RaplixaSpray device are approved for use in adults by the European Union (March 2015) and by the FDA (April 2015):

http://www.ema.europa.eu/ema/index.jsp?curl=pages/medicines/human/medicines/002807/human_med_001854.jsp&mid=WC0b01ac058001d124

<http://www.fda.gov/downloads/BiologicsBloodVaccines/BloodBloodProducts/ApprovedProducts/LicensedProductsBLAs/FractionatedPlasmaProducts/UCM445346.pdf>

Raplixa is indicated as an adjunct to hemostasis for mild to moderate bleeding in adults undergoing surgery when control of bleeding by standard surgical techniques (such as suture, ligature, and cautery) is ineffective or impractical. Raplixa is used in conjunction with an absorbable gelatin sponge (USP) and is applied directly or using the RaplixaSpray device (7).

Although there are physiologic differences in the levels of coagulation & fibrinolytic proteins over the maturation of children compared to adults, near adult levels are achieved by most children by 6 months of age, and these differences are considered to be physiologic, i.e., something that is normal, not due to anything pathologic nor significant in terms of causing illness (8, 9).

In current practice, typical fibrin sealants consist of human plasma-derived thrombin and fibrinogen that are filled and stored separately to avoid thrombin's enzymatic activity on fibrinogen before application to the intended site of action. In addition, most commercially-available products are stored frozen and must be thawed or reconstituted before they can be applied to a wound site. To improve the convenience and flexibility of use, Raplixa has been designed as a room temperature stable, ready-to-use powder fibrin sealant that dissolves and activates on contact when sprayed onto a bleeding or oozing wound site.

To date, there are 3 topical hemostats, Recothrom® and Tisseel® used in the adult population, that have also been approved by regulatory agencies as adjuncts to hemostasis in the pediatric population. These products were studied in very small pediatric populations (≤ 30 subjects) which simultaneously enrolled all subjects across age groups as they presented to clinical research centers. The efficacy and safety profile was similar to data observed in the adult population. There was no observation of enhanced immunogenic responses in the pediatric populations supporting the summary basis for approval. As Raplixa is a pharmacologically active topical hemostat approved for use in pediatric patients as are Recothrom® and Tisseel®, it is expected that Raplixa will have a similar safety, efficacy, and non-immunogenic profile in pediatric patients as Raplixa treatment in the adult population.

1.1.1. Preclinical Studies

Raplixa was shown to be effective in multiple animal models of mild and moderate surgical bleeding. The use of Raplixa was effective alone, but appeared to be enhanced in certain models when used in combination with a pressure sheet. Raplixa was locally and systemically non-toxic, and did not promote intra-abdominal adhesion formation when applied to non-target organs. In addition, the RaplixaSpray device was shown to have a low risk of producing air emboli when used correctly and incorrectly during hepatic resection surgery. The nonclinical efficacy and safety data generated support the clinical development of Raplixa and the RaplixaSpray device to promote hemostasis in surgical bleeding. For additional information please refer to the Investigator's Brochure (IB) and the Raplixa package insert.

1.1.2. Clinical Studies

Two Phase 2 trials (Verhoef, et al) (10) and one Phase 3 trial (Bochicchio, et al) (11) have been performed in different surgical indications to evaluate the efficacy and safety of Raplixa. The trials were performed in accordance with the clinical trial designs recommended by the CHMP for fibrin sealants (Guideline on the Clinical Investigation of Plasma Derived Fibrin Sealant/Haemostatic products; CPMP/BPWG/1089/00) and the FDA (Guidance for Industry: Efficacy Studies to Support Marketing of Fibrin Sealant Products Manufactured for Commercial Use, May 1999).

The clinical safety and efficacy of Raplixa were initially evaluated in 2 Phase 2 studies (FC-002 US and FC-002 NL) in surgical indications where adjuncts to hemostasis are required to control bleeding: spinal surgery, major hepatic resection, and peripheral vascular surgery (i.e., peripheral arterial bypass surgery and arteriovenous graft formation for hemodialysis access). Each of these types of surgery is characterized by diffuse and difficult to control, mild to moderate bleeding, frequently requiring the use of adjuncts to hemostasis.

In FC-002 NL, 56 subjects undergoing hepatic resection surgery were randomized 2:1 to receive Raplixa plus gelatin sponge (n=39) or gelatin sponge alone (n=17). In the Intent-to-Treat (ITT) analysis, a statistically significant reduction in the meantime to hemostasis (TTH) was observed with Raplixa, as compared to gelatin sponge alone (2.2 minutes vs 4.4 minutes, p=0.004). In FC-002 US, 70 subjects undergoing spinal, vascular, or general surgery were randomized 2:1 to Raplixa plus gelatin sponge (n=47) or gelatin sponge alone (n=23). A statistically significant reduction in the mean TTH was also observed with Raplixa in the ITT analysis, as compared to gelatin sponge alone (1.9 minutes vs 4.8 minutes, p<0.001).

The safety profile of Raplixa plus gelatin sponge across both FC-002 studies (n=86) was considered acceptable. The most common (>10% of subjects) treatment-emergent adverse events (TEAEs) being post-operative pain, constipation, nausea, edema, vomiting and hypokalemia. The majority of TEAEs were classified as mild or moderate in intensity. Thirty-five treatment-emergent serious AEs (TESAEs) were reported, with 25 reported from subjects undergoing liver resection surgery and only one considered possibly related to Raplixa by the Investigator. There were no observed Raplixa-associated trends or safety signals related to changes in vital signs, physical examinations, coagulation laboratory parameters or anti-thrombin neutralizing antibodies.

A total of 721 subjects undergoing hepatic resection, spinal surgery, vascular surgery and soft tissue dissection surgery were randomized in FC-004, a Phase 3, international, multi-center, single-blind, controlled trial (11). All primary and secondary efficacy endpoints in this study were met, with the median TTH for each surgery type being significantly shorter with Raplixa plus gelatin sponge than with gelatin sponge alone (p<0.0001). In all surgical indications, a significantly higher proportion of subjects achieved hemostasis at 3 and 5 minutes after application with Raplixa plus gelatin sponge than with gelatin sponge alone (p<0.0001). Results of the Phase 3 study indicated that Raplixa and the RaplixaSpray device appeared to be safe and well tolerated. The adverse events (AEs) reported in the trial were consistent with those expected in subjects undergoing spinal, vascular, hepatic resection, and soft tissue dissection surgical procedures under general anesthesia and the nature of the subjects' underlying diseases.

1.1.3. Known and Potential Risks and Benefits

This is the first trial of Raplixa in a pediatric population. Raplixa and the RaplixaSpray device are approved for use in adults by the European Union (March 2015) and by the FDA (April 2015):

Contraindications for Raplixa use are as follows.

Do not use:

- Intravascularly.
- For the treatment of severe or brisk arterial bleeding.
- In patients known to have anaphylactic or severe systemic reactions to human blood products.

The Warnings and Precautions for Raplixa/RaplixaSpray device are as follows:

- Thromboembolic events may result from intravascular application of Raplixa.
- Air or gas embolism can occur when using air- or gas-pressurized sprayers to administer fibrin sealants. Operate the device according to the manufacturer's instructions.
- Raplixa may carry a risk of transmitting infectious agents, such as viruses, and theoretically, the Creutzfeldt-Jakob disease (CJD) agents, despite manufacturing steps designed to reduce the risk of viral transmission.
- Allergic type hypersensitivity reactions may occur. If allergic type hypersensitivity symptoms occur, discontinue administration immediately.

Please consult the United States Pharmacopoeia (USPI) for further information.

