4.2. INCLUSION CRITERIA

Subjects may be included in the study if they meet all of the following criteria:

1. Subject age is \geq 36 weeks gestational age at birth (for infants) through < 18 years of age at time of treatment.
2. Subject's legal representative (parent or guardian) has signed an institutional review board (IRB)-approved informed consent document.
3. If a subject is \geq 7 years old, or appropriate age as defined by local regulations, the subject may be required to have signed an IRB-approved assent document.
4. Subject is scheduled to undergo one of the surgical procedures described in the protocol.
5. If female and of child-bearing potential, subject has a negative pregnancy test on the day of surgery (baseline).
6. If subject is a sexually active male or a sexually active female of child-bearing potential, subject agrees to use a medically accepted form of contraception from the time of consent to completion of all of the follow-up study visits.

During Surgery Inclusion Criteria

1. Presence of mild or moderate bleeding/oozing.
2. TBS surface area of ≤ 100 cm².
3. Subject has not received any whole blood, fresh frozen plasma (FFP), cryoprecipitate, or platelets within 24 hours prior to study drug. Packed red blood cell (PRBC) transfusions are allowed.
4. Subject has no intra-operative complication other than bleeding which, in the opinion of the Investigator, may interfere with the assessment of efficacy or safety.

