4.3. EXCLUSION CRITERIA

Exclusion Criteria

Subjects will be excluded from the study if any of the following exclusion criteria apply prior to enrollment:

1. Gestational age of < 36 weeks at birth (for infants less than 6 months).
2. Subject has any clinically-significant congenital coagulation disorder (e.g., hemophilia A or B) that may interfere with the assessment of efficacy or pose a safety risk to the subject according to the Investigator.

3. Subject has baseline abnormalities of international normalized ratio (INR) > 2.5 or activated partial thromboplastin time (aPTT) > 100 seconds during screening that are not explained by current drug treatment (e.g., warfarin, heparin) or chronic disease state necessitating surgery (e.g., end stage liver disease).
4. Subject has aspartate aminotransferase (ASAT/AST) and alanine aminotransferase (ALAT/ALT) > 3 times the upper limit of reference range during screening, except for subjects undergoing liver resection surgery or with a diagnosis of liver disease where there is no upper limit for these analytes due to the nature of their disease.
5. Subject is unwilling to receive blood products or products derived from human blood
6. Subject has platelets < 100 x10⁹ PLT/L during screening, unless due to chronic disease state, e.g., liver disease/failure, necessitating surgery.
7. Subject has known antibodies or hypersensitivity to Raplixa or any of its components, other thrombin preparations, or coagulation factors.
8. Subject has known allergy to porcine gelatin.
9. Subject has medical, social, or psychosocial factors that, in the opinion of the Investigator, could impact subject safety or compliance with study procedures.
10. Subject is; 1) currently participating in another clinical study or 2) has participated in another clinical study within 30 days of screening or 3) plans to participate in a clinical study prior to completion of the 30-day follow-up period.

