5. TREATMENT OF SUBJECTS

5.1. STUDY DRUGS

5.1.1. Raplixa

Table 1: Investigational Product

Product Name:	Raplixa™ [Fibrocaps™ (PRO-0601)]
Dosage Form:	Dry powder
Unit Dose	1.0 g/vial
Route of Administration	Topical
Physical Description	White to off-white powder
Manufacturer	Nova Laboratories, Ltd

Raplixa is a ready-to-use powder consisting of a blend of spray-dried human plasma-derived fibrinogen and thrombin particles with trehalose and calcium chloride with a concentration of 79 mg fibrinogen and 699 international units (IU) thrombin per gram Raplixa (1 vial).

The RaplixaSpray device is classified as a Class II device in the US. The device has been designed and manufactured according to International Organization for Standardization (ISO) 13485:2003 and 21 CFR 820 compliant processes to achieve simple, rapid delivery in the surgical environment onto a bleeding/oozing site. The device complies with the requirements of Medical Device Directive 93/43/EC as revised by 2007/42/EC for investigational devices. The delivery device uses a ball bearing mechanism to mobilize and subsequently deliver Raplixa via the outlet to the target site when the operating button is pressed. A part of this airflow is vented off through the back of the device, while the remaining airflow is used to deliver the Raplixa to the bleeding surface in a narrow plume. The device is supplied with two interchangeable nozzles: one rigid (attached to the device) and one flexible nozzle designed for use in hard to reach bleeding sites. The surgeon may switch the nozzles prior to or during use depending on the location of the bleeding site.

Raplixa Preparation

Prior to surgery, 2 vials of Raplixa and 2 to 3 gelatin sponges will be in the operating room. At sites using the RaplixaSpray device, 2 RaplixaSpray kits that contain the device, flexible nozzle and air filter, one regulator with a hose assembly with site specific connectors (both supplied by the Sponsor), and a central air supply or medical grade pressurized air will be available in the operating room. The second RaplixaSpray device is used as a back-up as needed.

The RaplixaSpray device will be connected to an air filter that is connected to a regulator set to a pressure of 1.5 bar (22 pounds per square inch [psi]), which is connected to either a central air supply or to a tank containing medical grade pressurized air. A vial of Raplixa will

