6.2.1. Visit 1: Screening Period (Day -30 to Day 1)

The Screening Visit will take place within 30 days of surgery. Following informed consent, the following screening assessments and procedures will be done:

1. Allocation of a nine digit number, which is composed of the 6-digit site number and incremental subject number.
2. Documentation of:
 - a. Demography: date of birth, gender and ethnic origin.
 - b. Medical history, including bleeding and surgical history.
 - c. Concomitant medications.
 - d. Assess and record AEs.
3. Review of inclusion/exclusion criteria to confirm subject eligibility.
4. Blood samples drawn for screening clinical laboratory tests (results may be obtained from clinical laboratory tests measured for routine clinical care prior to consent provided they were measured within 30 days of surgery) and results reviewed prior to enrollment.
 - a. Hematology: includes RBC, hemoglobin, hematocrit, platelet count, and white blood cell (WBC) count with differential.
 - b. Coagulation: prothrombin time (PT), aPTT, INR.
 - c. Blood chemistry panel: sodium, potassium, blood urea nitrogen (BUN)/urea, creatinine, glucose, albumin, AST/ASAT, ALT/ALAT, total bilirubin.
5. Blood sample for immunogenicity testing (do not draw in infants < 6 months old).
6. Physical examination (PE).
7. Weight and height.
8. Vital signs (pulse rate, resting systolic and diastolic blood pressures [BP], and temperature).
9. If a subject is ineligible for the clinical trial, they will be deemed a screen failure and their demographic data and specific reason for ineligibility will be captured on the applicable eCRF page(s).

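### Exclusion 7 carries the blood-product contraindication of section 1.1.3 only in part, so a known severe reaction solely to another human blood product meets no fixed exclusion

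*Combined protocol and SAP*

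**What the plan says.** Section 1.1.3 (Known and Potential Risks and Benefits) lists three contraindications under an instruction not to use the product. The third reads: "In patients known to have anaphylactic or severe systemic reactions to human blood products". It does not limit the type of blood product.

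In section 4.3, and in the same words in the synopsis, the nearest criterion is exclusion 7: "Subject has known antibodies or hypersensitivity to Raplixa or any of its components, other thrombin preparations, or coagulation factors". Section 5.1.1 gives the components: "Raplixa is a ready-to-use powder consisting of a blend of spray-dried human plasma-derived fibrinogen and thrombin particles with trehalose and calcium chloride".

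Three other criteria come close:

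- Exclusion 5: "Subject is unwilling to receive blood products or products derived from human blood".
- Exclusion 9: "Subject has medical, social, or psychosocial factors that, in the opinion of the Investigator, could impact subject safety or compliance with study procedures".
- During-surgery criterion 4 (section 4.2): "Subject has no intra-operative complication other than bleeding which, in the opinion of the Investigator, may interfere with the assessment of efficacy or safety".

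The screening step in section 6.2.1, item 3, is described as "Review of inclusion/exclusion criteria to confirm subject eligibility". Section 6.2.2 repeats an eligibility review before the operation.

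**The concern.** A contraindication that depends on the patient's history works best as an eligibility criterion, because eligibility is settled from that list before anyone is randomized. Here the safety text and the list have different scope. Section 1.1.3 covers human blood products in general, while exclusion 7 names a subset.

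Two things are at stake. The first is exposure of a child in whom the protocol says the product should not be used, in what 1.1.3 calls the first pediatric trial of Raplixa. Treatment is a topical application during a single operation, and section 4.4.1 foresees no withdrawal from study drug, so selection is the natural point of control.

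The second is a smaller matter of trial conduct. If the contraindication is noticed only after the envelope is opened in the operating room, the child is randomized but untreated. Section 3.1 then has the child withdrawn and possibly replaced, while section 10.3.2.1 keeps every randomized subject in the ITT population. Screening the child out earlier avoids both outcomes.

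**Working it through.** No arithmetic applies, and the plan states no figure to reproduce. The check compares the contraindication with every criterion in sections 4.2 and 4.3 (6 inclusion, 4 during-surgery and 10 exclusion) and with the operating-room check in 6.2.2.

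**Test case.** A child has a known anaphylactic reaction solely to red cells, platelets or immunoglobulin, is willing to receive blood products, and is otherwise eligible.

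**Step 1: does 1.1.3 apply?** Yes. The reaction is severe and the product is a human blood product.

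**Step 2: does exclusion 7 apply?**

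| | Section 1.1.3, third item | Exclusion 7 |
|---|---|---|
| Severity | Anaphylactic or severe systemic only | Any known antibody or hypersensitivity |
| Products | Human blood products, no limit | Raplixa and components, other thrombin preparations, coagulation factors |

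Exclusion 7 is the stricter of the two on severity and the narrower on product. Fibrinogen and thrombin are inside it. Reactions to plasma or cryoprecipitate are arguably inside it through coagulation factors. Red cells, platelets and immunoglobulin are not among the components in 5.1.1, so the test case falls outside.

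**Step 3: does another fixed criterion apply?**

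- Exclusion 5 turns on willingness to receive blood products, not on a past reaction. It does show that the wide class of products was available as wording.
- Exclusion 8 is limited to porcine gelatin.
- During-surgery criterion 3 concerns certain blood products received in the 24 hours before study drug, and it allows packed red cells.
- The remaining fixed criteria (age, consent, procedure, pregnancy, contraception, bleeding grade, site area, laboratory values, coagulation disorder, other trials) address different matters.

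None applies on this ground.

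**Step 4: does a discretionary criterion apply?** Exclusion 9 can, because a known anaphylactic reaction is a medical factor bearing on safety; it depends on the investigator's opinion. During-surgery criterion 4 is also a matter of opinion and concerns a complication during the operation, not a reaction in the history.

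**Step 5: would the procedures bring the history to light?** Section 6.2.1 asks for medical history and names bleeding and surgical history. Section 7 covers ongoing issues and, beyond five years, only what is considered relevant to the current surgery or to Raplixa's mechanism of action. A past reaction to a blood product is not named in either place. The operating-room list in 6.2.2 covers recent blood products, bleeding, complications and site area.

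**Result.** The test case is contraindicated under 1.1.3, meets no fixed exclusion, and can be excluded under exclusion 9 by judgement.

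**The case against.** The strongest reply is that the protocol already forbids the use. Section 1.1.3 is explicit and refers investigators to the US labeling, and section 12.3 requires the study to be run as the protocol describes. Nothing in the documents permits giving Raplixa to such a child. Exclusion 9 is itself on the eligibility list, and a history named as a contraindication in the same protocol is a plain example of what it is for. The part of the contraindication closest to the product's own constituents is covered, and more strictly than 1.1.3 requires. On this view the point is one of harmonizing wording.

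Most of that stands, and it sets the size of the point. A reader might infer that the list would admit a contraindicated child, or that the protocol allows the exposure. The documents support neither. The child could be randomized only if the investigator overlooked both 1.1.3 and exclusion 9.

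A reader might also be tempted to measure the gap by counting how many criteria are silent on reactions, or by quoting the 2:1 allocation as a risk of exposure. Neither measures it. Most criteria have no reason to mention reactions, and the allocation ratio says nothing about how many such children would present.

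A contrast with the bleeding contraindication is also limited. That one is matched by a required entry condition ("Presence of mild or moderate bleeding/oozing"), but 6.2.2 leaves the grading of bleeding to the investigator, so some judgement enters there too.

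What survives is that the prohibition sits in the Introduction, while eligibility is decided from a list that does not repeat it in full.

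**Conclusion.** The point holds in a narrow form. Exclusion 7 carries the third contraindication only in part, and a known severe reaction solely to another human blood product is left to investigator judgement under exclusion 9 or to recall of 1.1.3. Priority is low: the affected group is probably very small, and the consequence in an individual child could be serious.

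This rests on two readings. One is that the components meant in exclusion 7 are those listed in 5.1.1. The other is that coagulation factors may extend to plasma and cryoprecipitate but not to red cells, platelets or immunoglobulin. If plasma and cryoprecipitate were held to be outside exclusion 7, the gap would be wider.

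The documents give neither the number of children with such a history nor their risk with Raplixa, so the effect cannot be quantified. The potential severity is taken from the wording of the contraindication, not from a risk figure. No sample size, power or analysis figure is affected.

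**What to change.** Add to exclusion 7, in section 4.3 and in the synopsis: *or known anaphylactic or severe systemic reaction to any human blood product*. The screening review in 6.2.1 and the pre-operative review in 6.2.2 both refer to eligibility, so they pick up the amended criterion and need no separate line.

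Optionally, name prior reactions to blood products in the medical history item of 6.2.1, so that the information is asked for.

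The cost is one phrase in two places and very few additional exclusions, with no change to sample size or analysis.
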